9.5 The type and duration of the follow-up of subjects after adverse events

Any SUSAR related to the IMP's will need to be reported to the Sponsor irrespective of how long after IMP administration the reaction has occurred.

9.6 Development safety update reports

The CI will provide (in addition to the expedited reporting above) DSURs once a year throughout the clinical trial, or on request, to the Competent Authority (FAMHP in Belgium), Ethics Committee and Sponsor.

The report will be submitted within 60 days of the Developmental International Birth Date (DIBD) of the trial each year until the trial is declared ended.

10 STATISTICS AND DATA ANALYSIS

10.1 Sample size calculation

The primary outcome is the change in EQ-5D-5L from baseline to 6 weeks.

In the paper of Baron et al (2009) they evaluate the short-term effect of 5% lidocaine medicated plaster versus pregabalin on the quality of life.⁵⁸ Baron et al. reported 0.12 (0.240) as the mean change (SD) for EQ-5D from baseline to 4 weeks in the 5% lidocaine medicated plaster group compared to 0.04 (0.235) in the pregabalin group or an effect of 0.08. According to Walters and Brazier (2005) the mean minimally important clinical difference (MICD) for the EQ-5D is 0.074 for all patient groups and 0.081 for the backpain patient group.⁵⁹ **We have therefore powered the study around this effect of 0.08.**

Based on these numbers we would need **173 patients per treatment arm** using an independent samples t-test to have 80% power to detect an effect of 0.08 assuming a standard deviation of 0.240 with an alpha of 0.05/2. We are interested in all 3 comparisons, between on one hand the systemic versus the topical treatment options (pregabalin versus capsaicin 8% patch, pregabalin versus lidocaine 5% patch), and on the other hand within the topical treatment options (capsaicin 8% patch versus lidocaine 5% patch - as they imply a considerable difference in cost). Given the fact that each group will be used twice in the comparisons we corrected the significance level with a factor 2 to keep the overall type I error at 5%.

In Haanpää et al.³⁶ and Baron et al. patient completion rates for the follow-up of 90% and 96% respectively are reported which seems - bearing in mind that the burden on the patients in follow-up assessments is extremely low in the proposed pragmatic trial - realistic to us. However, in the systemic treatment arm drop-out from the study medication will be considerable (due to side effects). Indeed, in Baron et al. 39 of 153 patients (25.5%) of the pregabalin group discontinued the study medication and Haanpää et al. reports 41 out of 277 (14.8%) of the pregabalin arm withdrawing from the study medication. If we combine the two studies, we get 80 out of 430 or 18.6% drop out rate. For capsaicin 8% patch the withdrawal from study medication was 6 out of 282 (2.1%) and for lidocaine 5% plaster 9 out of 155 (5.8%) withdrew. Hence, we anticipated an average drop-out rate between 5.8% and 18.6% of 12% for each treatment arm which implies 197 patients per treatment group. In total, we would need to randomize **591 patients** in a 1:1:1 way to the 3 treatment arms.

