3 OBJECTIVES AND ENDPOINTS / OUTCOME MEASURES

3.1 Primary objective

To determine if topical treatment with lidocaine 5% patch (daily administration) or capsaicin 8% patch (periodic administration – upon reoccurrence of pain symptoms) significantly improves health-related quality of life after 6 weeks of treatment compared to systemic (oral) treatment with pregabalin as standard of care in adult patients suffering from localized neuropathic pain across a wide variety of etiologies (LNP), with a duration between 1 and 24 months (subacute to chronic neuropathic pain).

We are interested in 3 comparisons, between on the one hand the systemic versus the topical treatment options (pregabalin versus capsaicin 8% patch, pregabalin versus lidocaine 5% patch), and on the other hand within the topical treatment options (capsaicin 8% patch versus lidocaine 5% patch - as they imply a considerable difference in cost).

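### Testing all three pairwise comparisons at 0.05/2 does not hold the overall type I error at 5%: with three equal arms it is 6.4%

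*Protocol*

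**What the plan says.** Section 3.1 (Primary objective) names three comparisons and ranks none below the others: "We are interested in 3 comparisons, between on the one hand the systemic versus the topical treatment options", followed by capsaicin against lidocaine, which is included because the two differ in cost. Section 10.1 (Sample size calculation) repeats the list: "We are interested in all 3 comparisons, between on one hand the systemic versus the topical treatment options".

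Section 10.1 plans for 80% power to detect 0.08 with a t-test, "assuming a standard deviation of 0.240 with an alpha of 0.05/2". It explains the divisor by "Given the fact that each group will be used twice in the comparisons" and concludes that "we corrected the significance level with a factor 2 to keep the overall type I error at 5" per cent.

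Section 10.3.2 (Primary outcome analysis) specifies one linear regression with treatment as predictor and adjustment for baseline. It states no global test as a gate, no order of testing and no other multiplicity step.

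**The concern.** How often an arm is reused does not give a valid divisor. The familywise error of a set of tests depends on how many hypotheses there are and how the test statistics are correlated. Dividing by 2 covers two tests, and this family has three.

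At stake is the error guarantee for the primary endpoint. The protocol states a rule, a reason for it and the error rate it achieves. If the rate is wrong, so is the pairing of 80% power with 5% overall error at 173 analysed per arm.

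**Working it through.** **Inputs** (section 10.1): difference 0.08, SD 0.240, power 80%, alpha 0.05/2 per comparison, three arms at 1:1:1, 12% drop-out.

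**1. Reproduce the sample size.** Normal approximation, two-sided 0.025:

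n = 2 × (0.240/0.08)² × (2.2414 + 0.8416)² = 18 × 9.505 = 171.1, so 172.

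The exact noncentral-t calculation gives 173 per arm (power 80.2%). Then 173/0.88 = 196.6, so 197, and 3 × 197 = 591. The stated figures reproduce. At two-sided 0.05 the answer would be 143, so the plan does use two-sided 0.025 per comparison.

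**2. Familywise error when all three arms are equal.** With equal arm sizes, the largest of the three pairwise |t| values follows the studentized range distribution:

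FWER = P(Q with 3 groups and df > √2 × t at 0.9875).

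At 173 per arm, df = 516 and t = 2.248, so the cut-off is √2 × 2.248 = 3.179 and FWER = 6.43%. At 197 per arm (df = 588) it is again 6.43%. One million simulated trials with separate t-tests gave 6.45%. These figures already allow for the correlation between comparisons that share an arm. Three independent tests would give 1 − 0.975³ = 7.3%.

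**3. Other configurations.**
- Exactly one pair equal: there is one true null hypothesis, so the error is 2.5%.
- The two pregabalin comparisons only, all arms equal: 4.6% by simulation. The factor 2 is sufficient for this family.

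**4. Power with single-step tests that hold 5%** (difference 0.08, SD 0.24). The Tukey level is 0.0191. The Bonferroni level is 0.05/3 = 0.0167.

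| Analysed per arm | at 0.025 | Tukey | Bonferroni |
|---|---|---|---|
| 173 (planned) | 80.2% | 77.2% | 75.6% |
| 177 (90% of 197) | 81.1% | 78.2% | 76.7% |
| 189 (96% of 197) | 83.9% | 81.2% | 79.8% |

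**5. Closed procedure.** With three arms, if any two pairwise null hypotheses are both true, all three arms are equal. The closed family is therefore the global null plus the three pairs. Testing the global null at 5% and then each pair at 5% controls the familywise error in every configuration. Simulation at 173 per arm gave:
- familywise error 5.0% with all arms equal and 5.0% with one pair equal;
- power for a difference of 0.08 of 84% when the third arm equals one of the two compared;
- power of 78.8% when the third arm is exactly midway, and just under 80% when it is at 0.03 or 0.05. Power is below 80% over about the middle third of the interval from 0 to 0.08.

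**The case against.** **The excess is small and conditional.** This stands. The 6.4% needs all three arms to be equal, and a reader might wrongly take it as the trial's error rate in every case. The comparisons of systemic with topical treatment hold 4.6%; the breach comes from adding capsaicin against lidocaine. Still, an overall 5% claim must at least hold when nothing differs, and here it does not.

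**An SAP may add a gate.** It may, and a single regression with treatment as predictor suits a global test. The point is not that the protocol is silent. It states a rule and a resulting error rate, and that statement stays false as written whatever a later document adds.

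**Power need not fall short.** This largely stands. The 12% in section 10.1 comes from withdrawal from study medication, while section 10.3.2 keeps such patients in follow-up and in the analysis. The same section 10.1 calls 90–96% completion realistic. Adjustment for baseline cannot be expected to raise the residual variance above that of the change score. A reader might infer that the trial is underpowered, but the protocol does not support that.

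**Results with p between 0.019 and 0.025.** A reader might infer that any such result would be wrongly declared significant. That holds only for Tukey single-step testing. Under the closed procedure, a pairwise p up to 0.05 counts once the global test is significant.

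**Conclusion.** The claim of 5% overall type I error in section 10.1 is wrong as written, and so is its reason. The familywise error is 6.4% when all three arms are equal, an excess of 1.4 percentage points. It is 2.5% when only one pair is equal. At the planned 173 analysed per arm, 80% power for each comparison and 5% overall error do not hold together with single-step tests: power is 77.2% or 75.6%, rising to about 77–81% at the follow-up the protocol expects.

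These figures assume equal arm sizes, a common SD of 0.240 and two-sided tests. Two-sidedness is not stated, but follows from reproducing 173. The point should be fixed. It invalidates neither the sample size nor the two comparisons with pregabalin.

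**What to change.** In sections 10.1 and 10.3.2, replace the factor-2 rule with the closed procedure: test the 2-df treatment effect in the primary regression at 5% and, only if it is significant, test each of the three pairwise contrasts at 5%.

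The cost is a few sentences and no patients. For comparison, reaching 80% with single-step tests would need 184 (Tukey) or 190 (Bonferroni) analysed per arm. There are two drawbacks to record. Power dips to a minimum of 78.8% at 173 per arm when the third arm lies in about the middle third between the two compared. Any Tukey simultaneous intervals shown alongside may occasionally include zero when the gated test is significant, so the text should say which one decides.

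If 0.025 per test is preferred, either restate the overall error as 6.4% when all arms are equal, or limit the confirmatory family to the two comparisons with pregabalin (4.6%) and report capsaicin against lidocaine outside it. Section 3.1 would then need the same distinction.

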10.2 Planned recruitment rate

The number of recruiting centers is 13 all of them officially recognized multidisciplinary pain centers (MPC). In general, each of the participating pain centers have indicated that they see at least 50 new patients suffering from NP on a monthly basis, and more than 500 on a yearly basis. Since more than 60% of these patients actually suffer from LNP and are eligible to participate in the study, this means that each center will be able to identify at least 30 possible patients on a monthly basis. Assuming a consent rate of 90% of which 5% will be screening failures we end up with 25 patients. Even in the worst case scenario where we should be able to include 3 to 5 patients every month during the recruitment period, this means that at least 45 new patients will be included nationwide

on a monthly basis in the study protocol.

It is therefore anticipated that we will be able to include the total number of patients (591 patients) in a time frame of maximum 18 months.

Currently there are no competing clinical studies ongoing nor planned in Belgium on the subject of topical treatment of LNP. In addition, currently there are no ongoing trials on the subject of NP in Belgium so there will be no risk of competing trials during our study period.

It will be of great importance that participating pain centers activate their network with surrounding hospitals, rehab centers and ambulatory centers to achieve high referral rates of patients recently diagnosed with LNP. Finally, primary care physicians will also be notified of this study to optimize referral.

10.3 Statistical analysis plan

10.3.1 Summary of baseline data and flow of patients

- Compare primary outcome quality of life (EQ-5D-5L) at baseline between the treatment arms. Means and standard deviations per treatment group will be reported.
- Compare pain, mood, sleep and functional status at baseline between the treatment arms using the different questionnaires (PI-NRS, Sleep-NRS, HADS, ISI, Utrecht Work Engagement Scale-9, Interference BPI and WPAI). Means and standard deviations per treatment group will be reported.
- Compare gender, level of education and family situation between the treatment arms. Proportions per treatment group will be reported.
- Compare the 3 stratifying variables hyperalgesia/allodynia (absent or not), spontaneous positive sensory phenomena (such as dysesthesia) (absent or not) and duration of pain (less than or more than 3 months) between the treatment arms. Proportions per treatment group will be reported.
- A consort flow diagram will be produced to get an overview of the number of patients available at each stage: eligibility, randomisation, allocation, discontinuation and follow-up.

10.3.2 Primary outcome analysis

The primary outcome EQ-5D-5L at 6 weeks will be compared between the 3 treatment arms in first instance using a linear regression model with treatment as a predictor and correction for quality of life at baseline. All patients in the study will be used in an intention-to-treat (ITT) analysis.

Patients who withdraw from the study medication are offered a different treatment option of topical or systemic treatment respectively. Following standard care practice patients on the pregabalin arm will be offered an alternative systemic drug (gabapentin) and patients on the topical arm will be offered a different topical drug (failing treatment with lidocaine 5% medicated plasters will be treated with capsaicin patches and otherwise) Cross-over between topical and systemic treatment is not allowed to maximally preserve the treatment

effect between the two methods. Non-compliers and withdrawals are followed up according to the protocol. Their data will be collected in the same way as for the adherers and in the analysis they will be considered in the initially randomised treatment arm.

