7.3 The randomisation scheme

Randomisation will be performed at day -21 to day -1. Stratified randomisation will be used. Stratification according to site and the 3 stratifying variables: hyperalgesia/allodynia (absent or not), spontaneous positive sensory phenomena (such as dysesthesia) (absent or not) and duration of pain (less or more than 3 months) will be applied to keep the treatment arms balanced per stratum variable.

We will use a **minimisation procedure to randomize**. Minimisation assures similar distribution of selected participant factors between study groups. The first participant is truly randomly allocated; for each subsequent participant the imbalance score is computed based on all previous allocations as well as the hypothetical allocation of the current patient to each treatment. The preferred treatment is then selected by choosing the treatment allocation associated with the smallest imbalance score.

The distance measure used to calculate the imbalance score is marginal balance. Marginal balance computes the cumulative difference between every possible pairs of level counts (i.e. the number of patients in that particular factor level).

The allocation of the new patient is then made at random with a heavy weighting in favour

of the intervention that would minimise imbalance (a probability of 0.75 will be used). The remaining probability is equally divided between the non-preferred treatments.

Method of implementing the allocation sequence

A web based randomisation system QMinim will be used.

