10.3.4 Procedure(s) to account for missing or spurious data

Most of the data is collected through the online platform. A deviation of max. 48 hours or 7 days will be allowed for the completion of the different assessments at every time point (weekly versus monthly).

 The proposed linear mixed model allows that subjects have missing values at certain time points as the model uses all available data points per subject. The missing value assumption of the model is Missing At Random which means that missing values can only be dependent on the observed responses which seems a reasonable assumption in this case.

The study coordinator follows up on the missing data and records any reasons for missing data in patient file (medical record) and the eCRF (OpenClinica).

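### The primary regression leaves out site and the three clinical factors used in the minimisation, so its standard errors may be too large and power above the planned 80% is given up

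*Protocol*

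**What the plan says.** Section 7.3 of the protocol sets out the allocation: "Stratification according to site and the 3 stratifying variables: hyperalgesia/allodynia (absent or not), spontaneous positive sensory phenomena", with pain duration (below or above 3 months) as the third clinical variable. The method is minimisation on marginal balance. The arm that gives the least imbalance is chosen with probability 0.75, and the rest is split equally between the other two arms. Section 10.2 gives the number of sites: "The number of recruiting centers is 13".

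Section 10.3.2 names the primary analysis of week-6 EQ-5D-5L: "a linear regression model with treatment as a predictor and correction for quality of life at baseline". Baseline EQ-5D-5L is the only covariate, and no reason is given for leaving out the four minimisation factors.

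Section 10.3.3 brings the factors in further down the hierarchy. The three clinical factors appear in sensitivity versions of the week-6 regression, in a list that also contains use of rescue medication, gender, education and family situation. Site appears only as a random effect in an extension of the secondary mixed model.

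Section 10.1 sizes the trial on an independent-samples t-test without covariates, at 173 per arm "to have 80% power to detect an effect of 0.08 assuming a standard deviation of 0.240 with an alpha of 0.05/2".

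**The concern.** Minimisation makes the arms more alike on the chosen factors than chance would. If such a factor predicts the outcome, the balance removes most of its contribution to the variance of the treatment contrast. A model that omits the factor still counts its variance as residual noise. The reported standard error is then larger than the true sampling variability of the estimate. The design has paid for balance, and the primary analysis does not collect the return.

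The protocol itself treats these factors as clinically relevant. Section 2 discusses pain duration, hyperalgesia and allodynia as possible predictors of response, and section 10.3.5 tests whether the stratifying variables modify the treatment effect. At stake are the width of the confidence intervals for the three pairwise comparisons and the chance of detecting a real difference.

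The analyses in 10.3.3 do not fill the gap. No listed model is designated as the week-6 analysis adjusted for exactly the design factors. The sensitivity list includes rescue medication, which is measured after randomisation and can be affected by treatment. The last item of 10.3.3 describes confounder adjustment with site as a random effect as being like the primary outcome analysis, which is not the model in 10.3.2.

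**Working it through.** **Inputs.** From section 10.1: difference 0.08, SD 0.240, alpha 0.05/2 = 0.025 per comparison (sidedness not stated; two-sided reproduces the figure), 173 per arm. From section 10.1 (dropout paragraph): 12% dropout, 197 per arm, 591 in total. From 7.3 and 10.2: four minimisation factors, probability 0.75, 13 sites. Assumed: R2, the share of residual variance (after baseline EQ-5D-5L) explained by site plus the three factors. The SD of 0.240 is taken as the residual SD before those factors are added.

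**The protocol's own figure.** With the exact noncentral t, 172 per arm gives 79.91% power and 173 gives 80.16%, so 173 reproduces. Then 173/0.88 = 196.6, rounded up to 197, and 3 × 197 = 591.

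**Effect of omitting the factors (normal approximation, near-perfect balance).** The critical value is z = 2.2414.

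- Reported SE of the unadjusted model: 0.240 × sqrt(2/173) = 0.0258.
- True SD of the estimate: 0.0258 × sqrt(1 − R2).
- True size of the unadjusted test: 2 × [1 − Φ(z/sqrt(1 − R2))].
- Power, unadjusted: Φ(0.08/true SD − z/sqrt(1 − R2)).
- Power, adjusted: Φ(0.08/true SD − z).

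Worked for R2 = 0.10, where sqrt(0.90) = 0.9487: the true SD is 0.0245 and 0.08/true SD is 3.268. The effective critical value is 2.2414/0.9487 = 2.363. Unadjusted power is Φ(0.905) = 81.7%; adjusted power is Φ(1.027) = 84.8%.

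**Patient equivalent.** Let n be the per-arm size at which the unadjusted test, with the same forced balance, reaches the adjusted power at 173. Equating the two power formulas gives sqrt(n/2) = sqrt(173/2) + z × (0.240/0.08) × (1 − sqrt(1 − R2)). For R2 = 0.10: 9.3005 + 6.7242 × 0.0513 = 9.6456, so n = 186.1. The excess is 13.1 per arm, or about 39 over three arms.

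| Assumed R2 | SE overstated | True size (nominal 2.5%) | Power unadjusted | Power adjusted | Patient equivalent on 519 |
|---|---|---|---|---|---|
| 0 | 0% | 2.5% | 80.5% | 80.5% | 0 |
| 0.05 | 2.6% | 2.1% | 81.1% | 82.6% | 19 |
| 0.10 | 5.4% | 1.8% | 81.7% | 84.8% | 39 |
| 0.15 | 8.5% | 1.5% | 82.4% | 86.9% | 60 |

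Scaled by 591/519 to the number randomised, the last column becomes about 22, 45 and 69.

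**Check by simulation.** Minimisation with probability 0.75 on 13 equally likely sites and three evenly split binary factors was simulated for 519 patients over 1,500 runs, with R2 shared equally between site and the clinical factors. At R2 = 0.10 the unadjusted model reported a mean SE of 0.0258 against a true SD of 0.0243, with size 1.4% and power 81.5%. The adjusted model reported 0.0246 against 0.0244, with size 2.1% and power 83.5%. The Monte Carlo standard error of a size near 2.5% is sqrt(0.025 × 0.975/1500) = 0.4 points, and that of a power near 82% is about 1 point, so the simulation agrees with the formulas in direction and rough size.

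**The case against.** The strongest reply is that nothing promised is lost. Section 10.1 plans on an unadjusted t-test with the full SD, and the unadjusted analysis reaches at least 80% for every R2 considered. This stands. A reader might infer that the trial is underpowered or that its false-positive rate is at risk; the protocol's figures support neither, because the error is on the conservative side. Nor is the treatment estimate itself less precise: in the simulation its true SD is almost the same with and without the factors. What differs is the reported standard error.

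It is also fair to say that R2 is unsupported. The remark in section 2 on short pain duration concerns response to capsaicin, not the share of variance in EQ-5D-5L. If R2 were 0.02, power would be 80.7% unadjusted against 81.3% adjusted. Adjusted week-6 analyses are prespecified in 10.3.3, so the dispute is about which one is primary. That does not answer the point, since 10.3.2 fixes the covariates of the primary model and so has not left them to the SAP.

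A larger patient equivalent is tempting: 591 × (1/(1 − R2) − 1) gives 31, 66 and 104 for R2 of 0.05, 0.10 and 0.15. That compares the adjusted analysis with a trial that has no forced balance. This trial has it, so those figures are too high.

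A reader might also set "All patients in the study will be used in an intention-to-treat (ITT) analysis" beside "The proposed linear mixed model allows that subjects have missing values at certain time points" and conclude that the primary regression discards patients without a week-6 value, and that the mixed model should replace it. The protocol does not support this as a defect. It never specifies a complete-case primary analysis, and such handling is commonly left to the SAP, which was not available. At the cited completion rates of 90% to 96%, 24 to 59 of 591 patients would lack a value, fewer than the 3 × (197 − 173) = 72 allowed for. Making the mixed model primary would be a debatable trade: with only a subject random effect, its week-6 contrast would depend on the assumed covariance structure and on later visits.

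**Conclusion.** The omission is plain in the text and unexplained, and its direction is certain whenever the factors are prognostic beyond baseline EQ-5D-5L: reported standard errors too large, intervals too wide, test conservative. The size is uncertain. Over assumed R2 of 0.05 to 0.15 the standard error is overstated by 2.6% to 8.5%, and about 1.5 to 4.5 points of power are forgone at 173 per arm. At R2 = 0 the loss is nil. The figures rest on close balance, on 0.240 as the residual SD and on a two-sided 2.5% level. This is a point of efficiency and interval width. It threatens neither the planned power nor the validity of a positive result, but it is worth correcting because the correction costs so little.

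**What to change.** In 10.3.2, define the primary model as week-6 EQ-5D-5L regressed on treatment, baseline EQ-5D-5L, the three minimisation factors as fixed effects, and site as a fixed or random effect (choose one in advance). State that rescue medication, being post-randomisation, does not enter this model. Keep the regression on treatment and baseline alone as a sensitivity analysis, and align the last item of 10.3.3 with the revised primary model.

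The cost is a sentence or two of text. All the variables are already recorded for randomisation, and the sample size need not change. With site fixed, the model spends 12 + 3 = 15 further degrees of freedom, leaving 500 instead of 515 residual degrees of freedom at 519 analysed, which is negligible.

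### The primary week-6 regression is complete-case although the plan says all patients are used, and the stated missing-data method does not reach patients lost before week 6

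*Protocol*

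**What the plan says.** Protocol section 10.3.2 compares week-6 EQ-5D-5L between arms "using a linear regression model with treatment as a predictor and correction for quality of life at baseline". It then says: "All patients in the study will be used in an intention-to-treat (ITT) analysis". On patients who stop study medication it adds: "Non-compliers and withdrawals are followed up according to the protocol". They are analysed in the arm to which they were randomised, and section 7.11 likewise keeps them in the study. No rule is given for a patient without a week-6 score.

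Section 10.3.4 is the section on missing data. It covers one model only, the linear mixed model, and justifies missing at random (MAR) on the ground that "missing values can only be dependent on the observed responses which seems a reasonable assumption in this case". Section 10.3.3 places that model among the secondary and sensitivity analyses. It uses all EQ-5D-5L measurements over 26 weeks and estimates the week-6 effect.

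The table in section 7.8 schedules EQ-5D-5L at baseline and at weeks 6, 10, 14, 18, 22 and 26. Section 7.7 schedules PI-NRS, sleep NRS, side effects and drug discontinuation weekly. Section 7.12 foresees patients who stop because of adverse events and refuse follow-up.

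Section 10.1 cites follow-up completion of 90% and 96% in two earlier trials. It then sets its sample-size allowance from withdrawal from study medication: "Hence, we anticipated an average drop-out rate between 5.8% and 18.6% of 12% for each treatment arm".

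**The concern.** A regression on one post-baseline value drops every patient who lacks that value. The primary analysis is therefore complete-case, whatever the sentence about all patients says. The missing-data method is attached to a different, secondary analysis.

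That secondary model has a gap of its own. Its MAR assumption conditions on observed EQ-5D-5L. A patient lost before week 6 has only a baseline value, so the model knows nothing about how that patient fared on treatment. If such losses follow side effects or persisting pain, and occur more often in one arm, both the regression and the mixed model compare selected patients. The weekly data that could explain early loss are collected and analysed as outcomes in their own right, but are not used to handle missing EQ-5D-5L.

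At stake is the primary contrast of an open-label trial sized on a difference of 0.08, close to the 0.074 that section 10.1 cites as minimally important.

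**Working it through.** **1. The plan's own sample size.** Inputs from section 10.1: difference 0.08, SD 0.240, alpha 0.025 (taken as two-sided), power 80%. The two-sample t-test needs 172.35, so 173 per arm. Then 173 / (1 − 0.12) = 196.6, so 197 per arm, and 3 × 197 = 591. All three figures reproduce.

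**2. Patients left out of the primary regression.** Number left out = 591 × m, where m is the proportion without a week-6 score. Power is for the t-test with n = 197 × (1 − m) per arm.

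| Assumed m | Source | Left out of 591 | n per arm | Power |
|---|---|---|---|---|
| 4% | 96% completion | 23.6, about 24 | 189.1 | 0.84 |
| 10% | 90% completion | 59.1, about 59 | 177.3 | 0.81 |
| 12% | sample-size allowance | 70.9, about 71 | 173.4 | 0.80 |

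Planned power is kept throughout. The issue is who is analysed, not how many.

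**3. Who the mixed model brings back.** There are two groups without a week-6 score:
- Patients who miss week 6 but answer at week 10 or later contribute to the week-6 estimate under MAR.
- Patients lost before week 6 contribute a baseline value only, so they add nothing of substance on the treatment effect.

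The protocol does not say how the missing patients would divide between the two. The week-6 window bears on it, and is given as 3 days in section 7.7, +2 days in the notes to 7.8, and 7 days for monthly assessments in 10.3.4.

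**4. Size of a possible bias.** If missing patients score g below observed patients with the same baseline, the complete-case difference shifts by about (m₁ − m₂) × g. Equal loss gives zero shift. With 10% v 4% and an assumed g of 0.04 to 0.12, the shift is 0.06 × 0.04 = 0.0024 to 0.06 × 0.12 = 0.0072.

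A simulation gives the same picture. Settings: two arms of 197, true difference 0.08, SD 0.24, baseline correlation 0.5. A weekly auxiliary correlates 0.5 to 0.7 with the week-6 residual, and worse auxiliary values make loss more likely (logistic slope 1.5, calibrated to each arm's rate). The correlations, the slope and the arm-specific rates are assumptions; none is in the protocol.

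| Loss, pregabalin v topical | Complete-case estimate of a true 0.08 |
|---|---|
| equal (7% or 12% in both arms) | about 0.080 |
| 10% v 7% | about 0.075 to 0.077 |
| 10% v 4% | about 0.070 to 0.074 |
| 18.6% v 5.8% (extreme case) | about 0.060 to 0.066 |
| 18.6% v 2.1% (extreme case) | about 0.052 to 0.061 |

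The standard error is about 0.021 at 10% v 4%, so the bias of 0.006 to 0.010 there is roughly 0.3 to 0.5 standard errors. Regression imputation by arm from baseline and the auxiliary returned about 0.080 in every row, with nearly the same sampling variation.

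**The case against.** **The intention-to-treat sentence is about treatment assignment.** In context it says that withdrawals and switchers are analysed as randomised, and for everyone with a score that holds. This stands, but the sentence also claims that all patients are used, and the model named beside it cannot do that.

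**The loss figures are easy to misread.** A reader might infer that 12% of patients, or 18.6% on pregabalin against 2.1% to 5.8% on the topicals, will lack a primary outcome. The documents do not support that. These are medication-withdrawal rates, and sections 7.11 and 10.3.2 keep such patients in follow-up. The completion figures point to 4% to 10%, and they are one rate per cited trial, not one per arm. No arm-specific rate of outcome loss is given, so 10% v 4% is an assumption and the withdrawal rates serve only as an upper bound for illustration.

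**Missing data are already addressed.** The regression is described as a first step, the mixed model estimates the same week-6 effect, and missing questionnaires are actively chased. A reader might infer that the mixed model recovers nobody; that is too strong, because it uses patients who answer later. It still leaves out early losses in any useful sense.

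**The imputation result is favourable by construction.** The auxiliary that drives loss in the simulation is also the imputation predictor. This stands: the simulation shows what is possible if the weekly data explain the loss, not what will happen.

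**Detail belongs in a statistical analysis plan.** The imputation specification does, and a separate plan, not at hand here, may contain it. The mismatch within section 10.3.2 is in the protocol's own text and does not depend on that plan.

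**Conclusion.** The point holds in a limited form. The primary regression is complete-case despite the claim that all patients are used. It omits about 24 to 59 of 591 patients if week-6 loss equals the 4% to 10% implied by the cited completion rates. The stated missing-data procedure belongs to a secondary model that does not help patients lost before week 6.

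Bias is conditional. It needs loss that differs between arms and is related to side effects or pain. A reader might conclude that the primary estimate is biased in pregabalin's favour. The documents do not establish this: the direction and size depend on arm-specific loss that the protocol does not give. If pregabalin loses more of its worse patients, the topical benefit is understated, modestly at 10% v 4% under the assumed correlations, and not at all at equal loss. The change is worth making because it is nearly free, not because a large error has been shown.

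**What to change.** Make the primary analysis the same baseline-adjusted regression on all randomised patients, after multiple imputation of week-6 EQ-5D-5L separately by arm. Use as predictors baseline and later EQ-5D-5L and the weekly PI-NRS, sleep NRS, side-effect and drug-discontinuation data. Keep the complete-case regression and the mixed model as sensitivity analyses. Add a delta-adjusted analysis in which missing scores are made progressively worse than MAR predicts, including by different amounts per arm. Attach the missing-data rule in section 10.3.4 to the primary model, and state one week-6 window.

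If the complete-case regression stays primary, describe its set as all randomised patients with a week-6 score, analysed as randomised, and report the imputed analysis beside it.

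The cost is a little more analysis work. No new data, visits or patients are needed, and the sample size does not change.
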